### **Study Aims for Adding F-AV-1451 PET:**

The overall goal of this addendum is to determine the effects of prior traumatic brain injury (TBI), and ongoing post-traumatic stress disorder (PTSD) on brain tau, and the longitudinal change of brain tau, measured with the tau specific ligand F-AV-1451 and positron emission tomography (PET) scanning.

This study will test the hypotheses that:

- The distribution of brain tau will correspond to the previously reported Braak & Braak staging;
- The brain tau in older subjects is associated with cognitive impairment and increased in the presence of brain amyloid  $\beta$  ( $A\beta$ ) deposition (measured by  $A\beta$  PET);
- A prior history of TBI is associated with increased brain tau relative to  $A\beta$  deposition, after controlling for age and Apoe4 gene status;
- Longitudinal changes of brain tau correlate with  $A\beta$  PET, cognition, and history of TBI.

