**Hypothesis 2:** For the first part of the hypothesis, episodic memory will be the primary outcome (other cognitive functions will be explored later). Linear regression models will be used to assess the association between 18F-AV-1451 uptake and cognitive function. The primary independent variable will be a global measure of 18F-AV-1451 uptake, although additional analyses will consider the Braak & Braak stage ROIs to see if there are regional differences in the association with cognitive function. Similar to the

repeated measures models for Hypothesis 1, these models will include potential confounders including age, education, and Apoe4 status. Model assumptions of normality of the residuals, constant variance, and linearity will be checked and transformations or non-linear models will be considered if needed. The first part of the hypothesis will be supported if higher  $^{18}\text{F-AV-1451}$  uptake is associated with worse cognitive function. For the second part of the hypothesis,  $^{18}\text{F-AV-1451}$  uptake will be considered the primary outcome variable while A $\beta$  deposition measured by florbetapir SUVR will be considered the primary independent variable. When considering global  $^{18}\text{F-AV-1451}$  uptake, linear regression models will be the analytic method. When considering the Braak & Braak stage ROIs, repeated measures regression models similar to those described in Hypothesis 1 will be used.

**Hypothesis 3:** The analysis for this hypothesis will build on the model that was used for the second part of Hypothesis 2. Previous history of TBI and its interaction with A $\beta$  deposition will be included in the model (in addition to A $\beta$  deposition and confounders such as age and Apoe4 status) to see if those with a previous history of TBI and A $\beta$  deposition have even higher  $^{18}\text{F-AV-1451}$  uptake than those without a previous history of TBI. The hypothesis will be supported if the interaction between history of TBI and A $\beta$  deposition is statistically significant and positive.

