**Power considerations:** For Hypothesis 1, assuming 50 individuals per group, we will have 80% power to detect a difference as small as 0.57 standard deviations assuming  $\alpha=0.05$  and a two-sided test. If we reduce  $\alpha$  to 0.01, we will still have 80% power to detect a difference as small as 0.69 standard deviations. Recent studies from AIBL [351] and ADNI [344] found effect sizes ranging from 0.71 to 2.2 when performing similar comparisons with A $\beta$  deposition with the smallest effect size between MCI and NL subjects in ADNI; we expect tau to have similar effect sizes when comparing groups, so we should have ample power to detect effects. For Hypothesis 2, using all 450 subjects across all of the studies, we will have 80% power to detect a correlation as small as 0.13, assuming  $\alpha=0.05$  (0.16 with  $\alpha=0.01$ ) between  $^{18}\text{F-AV-1451}$  uptake and cognition or A $\beta$  deposition and  $^{18}\text{F-AV-1451}$  uptake. If other variables account for 10-20% of the variability in the outcome, we will still have 80% power to detect an

association accounting for as little as 1.4-1.6% of the variability (2.0- 2.3% with  $\alpha=0.01$ ). For Hypothesis 3, we will have 80% power to detect a difference in correlation as small as 0.30 (0.36 with  $\alpha=0.01$ ) assuming the correlation in the group without a previous history of TBI is at least 0.1. For the longitudinal hypotheses involving correlations, we will have 80% power to detect a correlation as small as 0.21 (0.25 with  $\alpha=0.01$ ) between change in tau and A $\beta$  deposition or change in cognition, assuming 180 individuals. If other variables account for 10-20% of the variability in change the outcome, we will still have 80% power to detect an association accounting for 3.4-3.8% of the variability (5.0-5.6% with  $\alpha=0.01$ ) attributable to change in tau. When comparing those with and without a history of TBI, we will have 80% power to detect a difference as small as 0.91 standard deviations (1.13 standard deviations with  $\alpha=0.01$ ).

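### Hypothesis 3 is worded as more tau for a given Aβ level after TBI, but it is decided and powered only on the TBI-by-Aβ interaction, which is a different claim

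*Protocol*

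**What the plan says.** Protocol, Study Aims, third hypothesis: "A prior history of TBI is associated with increased brain tau relative to" Aβ deposition, controlling for age and Apoe4 status. Nothing in that bullet says that the slope of tau on Aβ differs by TBI history.

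Protocol, Analyses for Addendum Hypotheses, Hypothesis 3: the model extends the one for the second part of Hypothesis 2 (tau uptake regressed on florbetapir SUVR). "Previous history of TBI and its interaction with A"β deposition are added, alongside Aβ and the confounders. The stated purpose is to see whether people with both TBI history and Aβ have higher uptake than people without TBI history. The only decision rule is: "The hypothesis will be supported if the interaction between history of TBI and" Aβ deposition "is statistically significant and positive". The TBI coefficient is in the model, but no criterion uses it.

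Same section, Power considerations: "For Hypothesis 3, we will have 80% power to detect a difference in correlation as small as 0.30" (0.36 at α = 0.01), "assuming the correlation in the group without a previous history of TBI is at least 0.1". No detectable TBI difference in tau at a given Aβ level is stated for this hypothesis.

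**The concern.** More tau at a given Aβ level is a statement about the Aβ-adjusted TBI effect. A parallel upward shift of the TBI group satisfies it. A positive interaction is a statement about slopes: tau rises more steeply with Aβ after TBI. Either can be true without the other, so the criterion is neither necessary nor sufficient for the hypothesis as worded.

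This matters because the overall goal of the addendum is the effect of prior TBI and PTSD on brain tau, and Hypothesis 3 is the cross-sectional hypothesis in the aims that concerns TBI. The Rationale also mentions tau deposition after single TBI and in CTE, a route that need not scale with amyloid. If TBI acts that way, the plan would report Hypothesis 3 as unsupported while the effect it describes is present.

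**Working it through.** **Inputs from the Protocol.** Nine groups of about 50, 450 in all; under Study Design, two groups have TBI history (one cognitively normal, one MCI). That gives about 100 with TBI and 350 without, or 100 and 200 among veterans only. The phrases "using all 450 subjects across all of the studies" (stated for Hypothesis 2) and "and a two-sided test" (stated for Hypothesis 1) are assumed to carry over to Hypothesis 3.

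**Step 1: reproduce the stated power.** Fisher z comparison of two independent correlations, reference 0.1:

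- SE = √(1/97 + 1/347) = 0.1149; atanh(0.1) = 0.1003.
- α = 0.05: tanh(0.1003 + (1.960 + 0.842) × 0.1149) − 0.1 = 0.299 (stated 0.30).
- α = 0.01: tanh(0.1003 + (2.576 + 0.842) × 0.1149) − 0.1 = 0.356 (stated 0.36).

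Of the splits tried, only 100 vs 350 gives both figures; 100 vs 200 gives 0.320 and 0.381. The stated power is therefore arithmetically sound, and it concerns effect modification only. (A difference in correlation matches a slope interaction only if the variances are similar in the two groups.)

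**Step 2: a uniform TBI effect under the present rule.** Assumptions that are not in the Protocol: tau = 0.3 × Aβ + δ × TBI + error, Aβ standardised with the same distribution in both groups, residual SD 1. Two-sided 0.05 with a positive sign, 10,000 simulations per row (6,000 for the 0.35 SD row).

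| δ (SD) | n | Rule met (interaction) | Aβ-adjusted TBI effect detected |
|---|---|---|---|
| 0.33 | 100/350 | 2.4% | 83% |
| 0.5 | 100/350 | 2.3% | 99% |
| 0.8 | 100/350 | 2.4% | 100% |
| 0.35 | 100/200 | 2.4% | 81% |
| 0.5 | 100/200 | 2.7% | 98% |
| 0.8 | 100/200 | 2.2% | 100% |

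The third column is simply the upper-tail size of the interaction test. With no interaction it stays near 2.5% whatever δ is.

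**Step 3: the other direction.** With a slope difference of 0.35 and no TBI shift at mean Aβ, the rule is met about 86% of the time at 100/350. With a slope difference of 0.4 and tau 0.35 SD lower at mean Aβ after TBI, it is met about 90% of the time (94% at 100/350, 88% at 100/200). In that case the two lines cross at 0.35/0.4 = 0.875 SD above mean Aβ, so TBI goes with less tau over most of the Aβ range.

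**Step 4: detectable TBI effect at mean Aβ, 80% power.** (z for α + 0.842) × √(1/n₁ + 1/n₂), in residual SDs:

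- 100/350, two-sided 0.05: 2.802 × 0.1134 = 0.32.
- 100/200, two-sided 0.05: 2.802 × 0.1225 = 0.34.
- At 0.025, the first Holm step: 3.083 × 0.1134 = 0.35 and 3.083 × 0.1225 = 0.38.

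**Step 5: cost of sharing alpha.** Power for a 0.35 SD shift alone at 100/350 is Φ(0.35/0.1134 − 1.960) = Φ(1.13) = 87% unadjusted and Φ(0.35/0.1134 − 2.241) = Φ(0.85) = 80% at the first Holm step. A slope difference of 0.35 per SD of Aβ behaves almost identically (about 86% and 80%). At 100/200 the shift has Φ(0.35/0.1225 − 2.241) = Φ(0.62) = 73%.

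**The case against.** The strongest reply is that effect modification was meant all along. The Rationale concludes that TBI may worsen amyloid-related tau; the analysis rule and the power paragraph both follow that idea; and the phrase about tau relative to Aβ can be read as more tau per unit of Aβ. Aβ is not among the controls listed in the aim. On that view one bullet is loosely worded and the rest is coherent. This stands in part: the phrase is ambiguous. It does not remove the point. The more natural reading of the aim concerns level, and the purpose sentence under Hypothesis 3 also compares levels. If modification alone is meant, the aim itself needs rewording.

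The second reply is that the simulation cannot show which claim was intended, since an interaction test with no interaction rejects at its nominal rate by construction. That is correct. The simulation shows only the consequence of the mismatch and the power that the design has for the unused test.

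A reader might infer that the plan would give the wrong answer to the whole TBI question. The Protocol does not support that. The TBI term is already in the Hypothesis 3 model, the Hypothesis 1 veteran model estimates the impact of TBI on uptake (with no Aβ term listed), and the longitudinal analysis compares tau change by TBI history. A uniform effect would be estimated and seen; what goes wrong is the formal Hypothesis 3 verdict.

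**Conclusion.** The mismatch is real and should be fixed, but it is not fatal to the study. The aim, read naturally, concerns tau level at a given Aβ; the sole support criterion and the stated power concern a difference in slope. Under the assumed model, a uniform TBI increase of 0.35 to 0.8 SD is labelled unsupported about 97 to 98% of the time, while the Aβ-adjusted TBI effect has 80 to 100% power. A positive interaction can also be called support when TBI does not raise tau at mean Aβ.

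The near-97% failure does not depend on the split or the effect size; it follows from testing a term that is zero. The detection figures do rest on the group sizes and on equal Aβ distributions. If Aβ differs between the TBI groups, the adjusted TBI effect is estimated less precisely.

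**What to change.** Split Hypothesis 3 into two named claims, both taken from the same model with Aβ centred:

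- (a) TBI history is associated with higher tau at mean Aβ: the TBI coefficient, adjusted for Aβ, age and Apoe4.
- (b) TBI amplifies the Aβ–tau association: the TBI-by-Aβ interaction.

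Give each its own criterion and share alpha by Holm. State the detectable effect for (a) beside the existing 0.30 difference in correlation: about 0.32 SD at 100 vs 350, or 0.34 SD at 100 vs 200 veterans, at unadjusted two-sided 0.05, and slightly larger under Holm.

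Do not test (b) only after (a) succeeds. At 100 vs 350 with a slope difference of 0.35, that order cuts the interaction's power from about 86% to 2% if there is no shift at mean Aβ, to 22% with a 0.15 SD shift, and to 75% with a 0.35 SD shift.

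Alternatively, if only effect modification is meant, reword the aim to say so and state that a null interaction will not be read as no TBI effect on tau.

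Cost: wording only, with no extra subjects or scans. Sharing alpha lowers power for either claim alone from about 86–87% to about 80% at 100 vs 350, for a 0.35 SD shift or a 0.35 slope difference.

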## **Discontinuations**

### ***Discontinuation from the Protocol Addendum***

- Participants may discontinue participation in this protocol addendum for any reason; this will not affect their participation in either the DOD-ADNI or ADNI2 study (depending on which they are currently enrolled).
- Participants who exhibit hypersensitivity to F-AV-1451 or any of its excipients are to be discontinued from this protocol addendum and are not to have another F-AV-1451 dose administered;
- Females of child-bearing potential who have a positive urine pregnancy test (HCG) will be discontinued from this protocol addendum and are not to have another F-AV-1451 dose administered.

- $^{18}\text{F}$ -AV-1451 was positive in the in vitro hERG (human ether-à-go-go-related gene) assay, with an  $\text{IC}_{50}$  of 0.610  $\mu\text{M}$ . This represents at least a 42 fold safety margin compared to the theoretical maximum plasma concentration that could be associated with the maximum human dose of 20 $\mu\text{g}$  in 5.2 L of blood. Additionally, in vivo cardiovascular assessments in dogs showed no evidence of QT prolongation. Nonetheless, a participant will be discontinued from the protocol addendum if it becomes necessary for the patient to start taking a medication known to prolong QT interval prior to performance of the baseline  $^{18}\text{F}$ -AV-1451 scan.

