#### ***Discontinuation or Holding of $^{18}\text{F}$ -AV-1451 dose:***

The dose of  $^{18}\text{F}$ -AV-1451 will be discontinued or held for the following reasons:

- Following baseline, a participant is not to receive the next scheduled  $^{18}\text{F}$ -AV-1451 dose should it become necessary for the patient to start taking a medication known to prolong QT interval and the patient is continuing to take the medication at the time of the scheduled  $^{18}\text{F}$ -AV-1451 scan;
- If, however, a participant receives a course of a QT-prolonging medication that is finished prior to a scheduled  $^{18}\text{F}$ -AV-1451 scan, the advisability of administering the next scheduled dose of  $^{18}\text{F}$ -AV-1451 and performance of the  $^{18}\text{F}$ -AV-1451 scan or holding the dose of  $^{18}\text{F}$ -AV-1451 should be considered by the investigator in consultation with the sponsor.

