#### **Addendum Design and Schedule:**

- Approximately 450 participants will participate in the  $^{18}\text{F}$ -AV-1451 PET addendum.
- ECG with results reviewed prior to  $^{18}\text{F}$ -AV-1451 dose administration.
- Approximately 450 subjects (50 from each cohort) who have consented to the Addendum will complete a Tau PET scan with  $^{18}\text{F}$ -AV-1451 PET scan at their next scheduled visit for DOD-ADNI and/or ADNI-2. For newly enrolled subjects enrolling in the DOD-ADNI study, the Tau PET scan will be performed at the baseline visit. Flortbetapir scans and the  $^{18}\text{F}$ -AV-1451 scans must be at least 16 hours apart; there is no maximum time limit to obtain the two scans.
- Up to 450 subjects (50 from each cohort) will be asked to do a follow-up Tau PET scan. The follow-up scan will be conducted 12 months after their initial scan.
- In the case of early discontinuation from the DOD-ADNI or ADNI-2 studies, the final  $^{18}\text{F}$ -AV-1451 PET scan will be obtained at the time of the early discontinuation visit if at least 3 months have passed since the most recent  $^{18}\text{F}$ -AV-1451 scan.
- Site investigators, patients, and caregivers will not be informed of the results of the  $^{18}\text{F}$ -AV-1451 PET scan results as they relate to the study; however, any findings that may be of potential medical concern will be provided for appropriate follow-up.
- Females of childbearing potential are to have a urine pregnancy test (HCG) on the day of the  $^{18}\text{F}$ -AV-1451 PET imaging session, before  $^{18}\text{F}$ -AV-1451 dose administration.
- $^{18}\text{F}$ -AV-1451 PET scans should be performed at least 16 hours apart from the  $^{18}\text{F}$ -flortbetapir PET scans due to the half-life of fluorine 18.
- Specific imaging acquisition protocols designed to ensure consistency across sites will be provided in an operations manual.

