**Longitudinal hypotheses:** Change in tau, as measured by differences between the time 2 and time 1 images will be the primary outcome when assessing associations with A $\beta$  deposition or history of TBI. A $\beta$  deposition (florbetapir SUVR) will first be considered as a continuous variable, though secondary analyses will compare change in tau in those that are A $\beta$  positive versus A $\beta$  negative. Linear regression, similar to that described above for Hypothesis 2, will be used to assess associations or differences between groups while adjusting for potential confounders of age and Apoe4 status. Finally, to assess associations between change in tau and change in episodic memory, the primary analytic strategy will use an extension of the repeated-measures, random effects models called simultaneous modeling, which utilizes the repeated-measures of both tau and episodic memory simultaneously in the same model. This technique allows for different observation times for the different outcomes, different predictors for each outcome (such as age, education, or Apoe4 status), and estimates of the between- and within-person variability. Model validation will be carried out using analytic and graphical techniques to check the core assumptions about linearity, homoscedasticity, multivariate normality, and independence of the within-person residuals beyond the person specific random effects. Hypotheses will be supported if there is a significant correlation between change in tau and change in episodic memory. Alternative strategies, if the simultaneous models do not converge, include linear regression models that use change in episodic memory as an outcome and change in tau as a predictor.

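### The primary amyloid and TBI analyses of tau change use only participants with both scans, which can bias them if loss of the second scan depends on baseline tau and baseline tau predicts change

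*Protocol*

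**What the plan says.** In the protocol's Analyses for Addendum Hypotheses, the paragraph on longitudinal hypotheses sets the outcome for the amyloid and TBI questions: "Change in tau, as measured by differences between the time 2 and time 1 images will be the primary outcome". Linear regression "will be used to assess associations or differences between groups while adjusting for potential confounders of age and Apoe4 status". Baseline tau is not a listed covariate.

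For tau change against memory change, the same paragraph chooses a random-effects model "which utilizes the repeated-measures of both tau and episodic memory simultaneously in the same model". Regression on change scores is only its fallback if that model does not converge.

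Second scans can be missing for reasons the protocol itself sets out:

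- **Discontinuation from the Protocol Addendum:** "Participants may discontinue participation in this protocol addendum for any reason". Participants with hypersensitivity "are to be discontinued from this protocol addendum and are not to have another" dose, and a positive pregnancy test has the same consequence.
- **Discontinuation or Holding of the dose:** after baseline, "a participant is not to receive the next scheduled" dose if a QT-prolonging drug has become necessary and "the patient is continuing to take the medication at the time of the scheduled" scan. After a finished course the scan is left to judgement.
- **Addendum Design and Schedule:** for those leaving the parent study early, the final "PET scan will be obtained at the time of the early discontinuation visit if at least 3 months have passed since the most recent" scan. People who leave sooner have no second scan.

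Study Design plans up to 450 repeat scans. Power considerations uses 180 for the longitudinal hypotheses.

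**The concern.** Amyloid and TBI are two of the three associations in the longitudinal hypothesis, the third being cognition. Both rest on complete pairs, while the cognition part uses a model that can keep incomplete pairs. The protocol gives no reason for the difference.

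A complete-pair regression is safe if loss depends only on variables in the regression. It is not safe if loss depends on baseline tau and baseline tau carries further information about change. The cohorts run from normal cognition to AD dementia, and the protocol's rationale ties severity of decline to tau. A link from illness to lost scans, and so to baseline tau, is therefore plausible, though assumed.

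If people with high baseline tau are lost more often, and high baseline tau goes with larger change, the regression loses observations where amyloid and change are both high. The slope is then attenuated. The TBI contrast is exposed in the same way if TBI groups have higher baseline tau.

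**Working it through.** **The plan's own figures.** These reproduce and are not in dispute. With the Fisher z formula, the smallest detectable r is tanh((z for alpha/2 + z for power)/√(n − 3)).

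- n = 180, alpha 0.05: tanh((1.960 + 0.842)/√177) = 0.208 (stated 0.21).
- n = 180, alpha 0.01: 0.251 (stated 0.25).
- TBI difference, two-sample noncentral t with 20 against 20: 0.909 and 1.130 SD (stated 0.91 and 1.13).

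**Mechanism.** Write A for amyloid, B for baseline tau and D for change, with D = βA + λe + noise, where e is the part of B not explained by A. Among people with both scans, E(D | A, kept) = βA + λE(e | A, kept). If keeping depends on B, then E(e | A, kept) varies with A and the slope on A is no longer β. If λ = 0 the extra term vanishes. If λ < 0 the bias changes sign.

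**Estimators compared.**

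- Complete-pair: slope from regressing D on A in those with both scans.
- Likelihood using all baselines: (slope of D on A given B, in completers) + (slope of D on B given A, in completers) × (slope of B on A, in all 450).

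**Amyloid, first set of assumptions.** n = 450, true standardised slope 0.30, correlation of amyloid with baseline tau 0.5, residual correlation of baseline tau with change 0.3-0.5, 57-79% re-scanned, loss logistic in baseline tau. None of these inputs except n comes from the protocol.

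| Log-odds of loss per SD of baseline tau | Odds ratio | Complete-pair slope | Bias |
|---|---|---|---|
| 0.5 | 1.6 | 0.29-0.295 | about 2-3% |
| 1.0 | 2.7 | 0.265-0.285 | about 5-12% |
| 1.5 | 4.5 | 0.24-0.27 | about 9-20% |

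The likelihood estimator averages 0.30 throughout, with the same or a slightly smaller standard error.

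**Amyloid and TBI, second set of assumptions.** True amyloid slope 0.21, TBI effect 0.30 SD, correlation of amyloid with baseline tau 0.5, baseline tau 0.5 higher with TBI.

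| Residual correlation | Loss | Odds ratio per SD | Amyloid slope | TBI effect |
|---|---|---|---|---|
| 0.2 | 20% | 2 | 0.206 (−2%) | 0.296 (−1%) |
| 0.4 | 20% | 3 | 0.188 (−10%) | 0.277 (−8%) |
| 0.4 | 60% | 3 | 0.172 (−18%) | 0.265 (−12%) |
| 0.6 | 60% | 5 | 0.120 (−43%) | 0.217 (−28%) |

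The last row is an extreme case. The estimator using all baselines stayed within about 3% of the truth in these settings. With residual correlation 0 there was no bias at any loss rate tried (10-60%). With residual correlation −0.3, amyloid-tau correlation 0.4, TBI shift 0.3, 60% loss and odds ratio 3, the estimates rose to 0.235 and 0.338.

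**Check on the replacement model.** Suppose a covariate has correlation r with amyloid and effect g on change (both assumed, in SD units). A repeated-measures model that carries the covariate only as a main effect does not adjust change for it, so even with complete data its predictor-by-time slope is β + r × g. That is 0.30 + 0.3 × 0.1 = 0.33 at one end and 0.30 + 0.4 × 0.3 = 0.42 at the other. The planned difference regression gives 0.30 there, and so does the repeated-measures model once covariate-by-time terms are added.

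**The case against.** **This is missing-data handling, which belongs in the SAP.** The protocol nowhere forbids imputation, weighting or sensitivity analyses, and a difference regression is compatible with them. Their absence here is not a finding. What stands is narrower: the protocol itself names the primary outcome and model, and as written that model has no outcome for a person scanned once.

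**The listed triggers are not about tau.** Hypersensitivity, pregnancy and a current QT-prolonging drug are not tau-based, and people on such drugs are already excluded at entry. A reader might infer from the stopping and holding rules that loss follows tau; the documents do not support that. Any link runs through general illness or cognitive decline and is an assumption.

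**Many early leavers are scanned.** The early-discontinuation scan recovers second scans from anyone leaving the parent study at 3 months or later. This reduces the loss, though it does not cover withdrawal from the addendum alone or held doses. The recovered scans can also span shorter intervals than 12 months.

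**The bias is small under moderate inputs.** With 57-79% re-scanned, the slope's standard error is about 0.05-0.06. A bias of 0.005-0.035 is then roughly 0.1-0.6 standard errors. This is correct and limits how much weight the point can bear.

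**Conclusion.** The point holds in conditional form. The primary amyloid and TBI analyses are complete-pair by construction, and they can be biased if two conditions hold together: loss depends on baseline tau, and baseline tau predicts change beyond the covariates. Under the assumed inputs, the amyloid bias is about 2-12% with moderate dependence and up to about 20% with strong dependence. The TBI bias is about 1-8% at 20% loss in the settings shown. Larger values need heavier loss or more extreme dependence.

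Two stronger readings are not supported. One is that loss does bias these associations, and always towards zero: the protocol establishes neither condition, and the bias can be absent or reversed. The other is that 180 of 450 is the expected retention, meaning 60% loss: the protocol does not explain the 180, so it is not a stated loss rate.

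The change is worth making because it costs very little and extends an approach the same paragraph already uses for memory. It is a recommended improvement, not an essential correction.

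**What to change.** In the longitudinal paragraph of Analyses for Addendum Hypotheses:

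- Make the primary amyloid and TBI analyses a likelihood repeated-measures model of tau at both scans, with an unstructured 2 × 2 covariance, including every participant with a baseline scan.
- Test the predictor-by-time term.
- Include age-by-time and Apoe4-by-time terms as well as the main effects, so that the model matches the difference regression when follow-up is complete.
- Keep the time 2 minus time 1 regression as a sensitivity analysis.
- Report the number without a second scan, and the reason, by cohort.

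The cost is analysis wording and a slightly more complex model; no new data or visits are needed. The model is valid when loss depends only on observed data (missing at random). If loss depends on the unseen second scan, both methods are biased, and the report of missing scans by cohort and reason lets readers judge that risk.
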